5.5.9.2. Continuous Safety Measures

Analyses of continuous safety data will be conducted on patients who have a baseline and at least 1 postbaseline observation for SP III.

For all the continuous safety measures (including planned laboratory measures, vital signs and weight, ECG intervals and heart rate), box-whisker plots with summary statistic tables for absolute value and change from baseline at scheduled visit and at endpoint (defined as the final postbaseline value) will be provided for SP III. The change from baseline results will be compared between treatment arms using the analysis of covariance (ANCOVA) model with treatment, pooled investigative site and baseline value in the model.

5.5.10. Subgroup Analyses

Subgroup analyses will be performed for primary efficacy measure (change from baseline on weekly number of cluster headache attack) only for the ITT patients in the SP III.

[Table CGAL.5.8](#) provides definitions for each subgroup variable. Subgroup variables are usually selected if they are potentially prognostic or predictive. A subgroup variable is prognostic if values of the subgroup variable predict the change in efficacy measures regardless of the treatment group assignment. A subgroup variable is predictive if values of the subgroup variable predict heterogeneous treatment effect. Demographic subgroup variables (sex, racial origin, ethnicity, age, and region) may neither be prognostic nor predictive, but they are standard subgroup variables needed for regulatory submission. Baseline average daily number of cluster headache attack category and sex were included in the dynamic allocation randomization algorithm and are considered possibly prognostic [CCI](#)

The purpose of the analyses for these subgroup variables is to assess the consistency of treatment effects across the different values of each subgroup variable.

[Table CGAL.5.9](#) summarizes the subgroup analyses to be conducted, using those subgroup variables presented in [Table CGAL.5.8](#).

Table CGAL.5.8. Definition of Subgroup Variables

Subgroup Variable	Categories
Sex	Male, female
Racial origin (combine those with less than 10%)	American Indian/Alaskan Native Asian Black/African American Native Hawaiian/Pacific Islander White Multiple
Ethnicity	Hispanic or Latino Not Hispanic or Latino
Age	<40 or \geq 40

Definition of Subgroup Variables

Subgroup Variable	Categories
Baseline average daily number of cluster headache attack category	1) ≤ 4 attack per day, > 4 attack per day 2) ≤ 3 attacks per day, > 3 attacks per day 3) ≤ 2 attacks per day, > 2 attacks per day
Region	Europe, North America (US and Canada)
CCI	

Table CGAL.5.9. Subgroup Analyses

Outcome Variable	Subgroup Variables	Analysis
EFFICACY VARIABLES		
1. Change from baseline to each postbaseline weekly interval up to Week 3 in the SP III for: Number of cluster headache attacks	Sex Racial origin Ethnicity Age Baseline average daily number of cluster headache attack category Region CCI	Repeated measures analysis using the model described in Section 5.5.8.1 with additional terms for subgroup, subgroup-by-treatment, subgroup-by-week, and subgroup-by-treatment-by-week interactions added to the base model.

Abbreviations: CCI

SP = study phase.

For the subgroup variable of race, all the categories that have less than 10% of the patients in the study will be combined in the analysis. CCI

For subgroup analyses, the subgroup-by-treatment and subgroup-by-treatment-by-visit/week interactions will be tested at a 2-sided 0.05 significance level. Treatment group differences will be evaluated within each category of the subgroup variable.

The subgroup analysis for change from baseline to each weekly interval up to Week 3 in number of cluster headache attacks will be conducted with repeated measures analysis. The same MMRM model as described in Section 5.5.8.1 will be used with additional terms of subgroup, subgroup-by-treatment, subgroup-by-week, and subgroup-by-treatment-by-week interactions added. In this analysis, the p-value for the subgroup-by-treatment, subgroup-by-week, and subgroup-by-treatment-by-week interactions will be reported.

For subgroup analysis, the LSMean and LSMean change estimate as well as the treatment comparisons within each subgroup will be analyzed with the data within that specific subgroup only.

5.5.11. Sensitivity Analysis

For all sensitivity analyses for the primary efficacy endpoint, the diary data up to Week 3 will be used.

Dynamic Allocation (Minimization) Assumption

A permutation test will be performed as a sensitivity analysis of the primary MMRM analysis to confirm the results of the asymptotic inference. The key features of the permutation test that will be employed are as follows:

- The patients' baseline covariates, responses, and enrollment order will be considered fixed.
- The sharp null hypothesis will be assumed, i.e., responses to galcanezumab and placebo will be assumed exactly equal.
- The exact minimization algorithm and exact site pooling algorithm will be used to generate the null distribution of the primary test statistic from the MMRM analysis.
- The p-value based on the generated null distribution (i.e., permutation test p-value) will be obtained by comparing the observed test statistic value to the percentiles of the generated null distribution.

Explicitly, the p-value is derived from the permuted distribution of test statistics as follows. If the total number of permutations is m , and b of these permutations have a test statistic greater than or equal to the observed test statistic, z , then the permutation p-value, p^p is,

$$p^p = \frac{b + 1}{m + 1}$$

where m equals 100 000. As discussed in Phipson and Smith (2010), this is an upper bound on the estimated p-value. This method is used to generate the approximate null distribution. Note that the described permutation p-value calculation should be conducted such that a positive value for the test statistic should indicate a favorable treatment effect galcanezumab 300 mg relative to placebo.

Missing Data Assumption

Sensitivity analyses will be performed to assess the robustness of the primary analysis conclusions to deviations from MAR assumption. The approach for these analyses is to vary the assumptions of missing data for the primary analysis in a systematic way. Basically, the method will be to predict the missing outcomes and then add a value (denoted as Δ_A) to the predictions in the active treatment group and another value (denoted as Δ_P) to the predictions in the placebo treatment group, consistent with the sensitivity approach suggested in Permutt (2015). This procedure will be repeated multiple times for different values of (Δ_A, Δ_P) using the following steps:

[figure not shown]
1. Predict the missing outcomes for each treatment via multiple imputation based on observed primary endpoint and baseline values. Such imputation will be carried out using a Markov Chain Monte Carlo method with a Jeffreys prior via SAS® PROC MI. Thirty (30) such imputations will be created.
2. Add Δ_A to the imputed values for patients taking active treatment and Δ_P to the imputed values for patients taking placebo.
3. Conduct the primary analysis separately for each of the 30 imputations.
4. Combine the results of these analyses using Rubin's combining rules, as implemented in SAS® PROC MI ANALYZE.

The above steps will be repeated multiple times for different values of (Δ_A, Δ_P) with Δ_P ranging from (0, twice the absolute value of the mean value seen for placebo in the primary analysis) and Δ_A ranging from $(\Delta_P, \Delta_P + \text{absolute value of the mean treatment difference seen within the primary analysis})$. For example, if the mean change from baseline for placebo is -3.6 and the corresponding treatment difference is -1.5, then Δ_P would range from (0, 7.2) and Δ_A would range from $(\Delta_P, \Delta_P + 1.5)$.

Normality Assumption

To assess the robustness of the MMRM results to deviations from normality assumption, a sensitivity analysis for raw number of cluster headache attacks (total number of cluster headache attacks for each interval without imputing missing value and without normalization to 7-day period) will be conducted with a repeated measures negative binomial regression model fitted with SAS PROC GLIMMIX. The model will include treatment, gender, pooled investigative site, weekly time period (Week 1, Week 2, Week 3), and treatment-by-time-period interaction, as well as the continuous fixed covariates of baseline value, and log (number of compliant days within each weekly time period divided by 7) as the offset in the model. In case of nonconvergence, pooled investigative site may be excluded from the model. Directional consistency of treatment effects from this model and the primary analysis MMRM model as specified in Section 5.5.8.1 will be examined.

In addition, as another form of sensitivity analysis, residuals from the primary analysis MMRM model will be examined and outliers identified. Consistency of results before and after removing patients with outlier residuals will be examined.

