- Addition of analysis for change from baseline in total weekly dose of sumatriptan Sc, sumatriptan nasal spray, and zolmitriptan nasal spray separately as well as combined.

Statistical Analysis Plan Version 3 was approved prior to IA1. The changes incorporated in Version 3 are as follows:

- Posttreatment follow-up phase safety analyses will have only 1 baseline.
- A section on protocol violations to be identified was added.
- Sensitivity analyses were updated, to be consistent with other Phase 3 studies of LY2951742.
- Infections section will only deal with upper respiratory tract infections; analyses were modified to be consistent with other Phase 3 studies of LY2951742.
- For Columbia-Suicide Severity Rating Scale (C-SSRS), 1 bullet was split into 2 to enhance readability, and baseline definition for improvement from baseline analysis was clarified.

- Criteria for sustained elevation in diastolic blood pressure was changed to be consistent with the single time point analysis.
- An additional criteria threshold for QTc increase was added.
- Analyses of elevations in hepatic laboratory tests were clarified, and an additional subset was added.
- Immunogenicity analyses were updated to be consistent with other Phase 3 studies of LY2951742.
- An additional subgroup analysis category, for age, was added.
- Some minor corrections and clarifications were made.

Statistical Analysis Plan Version 4 was approved after the last patient was randomized and prior to interim analysis (the first and final assessment of primary efficacy endpoint after all patients completed double-blind phase, which is the first unblinding to study team). Enrollment in the trial was terminated (due to enrollment infeasibility) prior to reaching the sample size target for the originally planned interim analysis. Therefore, the planned interim analysis for sample size re-estimation did not occur.

In the SAP Version 4, the updates were made mainly for incorporating the recent learnings from migraine data or for consistency across the galcanezumab program. The changes incorporated in Version 4 of the SAP are summarized as follows:

- LY2951742 was replaced by galcanezumab in the body of the SAP.
- Consistent with the primary endpoint and analysis methodology for the pivotal migraine studies, the primary endpoint was updated to be the overall treatment effect over the Weeks 1 to 3 during the double-blind treatment phase, rather than the treatment effect at the single time point, Week 3.

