5.4.1.2. Derived Variables for Cluster Headache Attacks

In Study CGAL, for primary measure of cluster headache attacks, the daily data for each patient (including last 7 days in the eligibility report [prerandomization diary phase], 8 weeks of daily

data during treatment) will be converted into 9 roughly 7-calendar day intervals: the baseline 7-day interval, Week 1, 2, 3, 4, 5, 6, 7, and 8. Each day, the patient may report zero, 1, or multiple cluster headache attacks. Any ePRO diary data reported beyond the protocol defined collection period will not be used for statistical analysis.

The approach to split the postbaseline data into weekly intervals is done as follows:

- Firstly, postbaseline daily data will be split into Weeks 1 to 4 versus Weeks 5 to 8 using 1st and 2nd injection date. All data \geq 1st injection date and $<$ 2nd injection date will be considered as Weeks 1 to 4; all data \geq 2nd injection date and $<$ treatment phase disposition date will be considered as Weeks 5 to 8. If 2nd injection date is missing, then all the data before treatment phase disposition date will be put into Weeks 1 to 4.
- Secondly, data within Weeks 1, 2, and 3 will be determined using calendar days. In other words, the 1st injection date will be considered as Day 1, then Days 1 to 7 will be Week 1; Days 8 to 14 will be Week 2; Days 15 to 21 will be Week 3. Week 4 will include all the data from Day 22 to the date before the 2nd injection (or before the treatment phase disposition date if second injection date is missing).
- Thirdly, if the 2nd injection date is not missing, the data within Weeks 5, 6, 7, and 8 will be determined using calendar days. In other words, the 2nd injection date will be considered as Day 1, then Days 1 to 7 will be Week 5; Days 8 to 14 will be Week 6; Days 15 to 21 will be Week 7. Week 8 will include all the data from Day 22 to the date before the treatment phase disposition date.

For each weekly interval, the following missing data imputation method will be used:

- 1) if there are less than or equal to 3 days with nonmissing answer to cluster headache attack frequency in the weekly interval; or 2) the diary compliance rate is less than or equal to 50%, then the weekly interval will be considered missing;

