5.5.1.2. Handling of Dropouts or Missing Data

Repeated measures analyses will be used as the statistical approach for handling missing data. The model parameters are simultaneously estimated using restricted likelihood estimation incorporating all of the observed data. Estimates have been shown to be unbiased when the missing data are missing at random and when there is ignorable non-random missing data (Mallinckrodt 2008). Missing at random (MAR) assumption will be evaluated using sensitivity analyses as defined in Section [5.5.11](#).

Approaches for Handling Missing Data for Derivation of Cluster Headache Attacks Derived from ePRO per 7-Day Interval

In Study CGAL, to derive the number of cluster headache attacks per 7-day interval, the daily data for each patient (including the last 7 days in the eligibility report [pre-randomization diary phase] and the 8 weeks of daily data during treatment) will be converted into 9 roughly 7-calendar day intervals: the baseline 7-day period, Weeks 1, 2, 3, 4, 5, 6, 7, and 8. Each day, the patient may have zero, 1, or multiple cluster headache attacks. For each weekly interval, the following missing data imputation method will be used:

- 1) if there are less than or equal to 3 days with nonmissing answer to cluster headache attack frequency in the weekly interval; or 2) the diary compliance rate is less than or equal to 50%, then the weekly interval will be considered missing;
- Otherwise, 1) if there are greater than or equal to 4 days with nonmissing answer to cluster headache attack frequency in the weekly interval; and 2) the diary compliance rate is greater than 50%, then the average number of cluster headache attacks across the non-missing days will be used to impute the missing days.

For detailed example about missing data imputation, please see Section [5.4.1.2](#).

Then the change from baseline to Weeks 1, 2, 3, 4, 5, 6, 7, and 8 will be derived.

The same approach will also be applied to secondary and exploratory efficacy measures that derived from ePRO data.

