5.6. Interim Analyses

Up to 2 interim analyses were planned for Study CGAL. Interim analysis 1 during SP III may be conducted that may result in increasing the sample size or stopping the trial for futility. Details were documented in the Statistical Analysis Center SAP, ERB supplement, and DMC Charter. However, this interim analysis for sample size re-estimation will not happen due to enrollment infeasibility. The DMC will still independently monitor patient safety during this trial.

The other interim analysis that was planned will be conducted after all patients have had the opportunity to complete 8 weeks of treatment (SP III) and, thus, will be the final analysis of the primary efficacy endpoint. The interim analysis will be conducted using internal unblinded study team members who do not have direct interaction with sites.

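### The missing-data sensitivity grid limits the active-arm penalty to the placebo penalty plus the observed effect, so it can pass in full without showing how far the result is from tipping

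*SAP*

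**What the plan says.** SAP 5.5.1.2 relies on the repeated-measures model for missing data and states: "Missing at random (MAR) assumption will be evaluated using sensitivity analyses". SAP 5.5.11, under Missing Data Assumption, gives the purpose: "Sensitivity analyses will be performed to assess the robustness of the primary analysis conclusions to deviations from MAR assumption".

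The procedure has four steps. Step 1: "Predict the missing outcomes for each treatment via multiple imputation based on observed primary endpoint and baseline values", with 30 imputations. Step 2 adds Δ_A to the imputed active values and Δ_P to the imputed placebo values. Steps 3 and 4 run the primary analysis on each imputed set and combine the results by Rubin's rules.

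The grid is then fixed:

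- Δ_P runs from 0 to twice the absolute placebo mean change.
- Δ_A runs from Δ_P to Δ_P plus the "absolute value of the mean treatment difference seen within the primary analysis".

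The SAP illustrates this with "if the mean change from baseline for placebo is -3.6 and the corresponding treatment difference is -1.5", which gives Δ_P from 0 to 7.2 and Δ_A from Δ_P to Δ_P + 1.5.

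The readable text gives no step size, no instruction to widen the range until the conclusion changes, and no request for a tipping boundary. One figure in this section is not visible and a redacted section follows it; neither is counted here as an omission. The other sensitivity analyses in 5.5.11 (permutation test, negative binomial model, outlier removal) do not vary the missing-data assumption.

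**The concern.** Imputation is done within each arm, so under MAR a missing active patient is imputed with roughly the active-arm benefit. The harshest penalty allowed at any Δ_P removes that benefit and brings the two arms' imputed means to about the same level. The grid never asks what happens if missing active patients do worse than that while missing placebo patients stay near their MAR prediction. The permitted gap is also tied to the observed effect, so a smaller effect gets a narrower band.

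Weeks 1-3 values can go missing in ways that may be related to outcome. One is poor diary completion (SAP 5.4.1.2): "the diary compliance rate is less than or equal to 50%, then the weekly interval will be considered missing". The same happens with three or fewer diary days. Another is leaving the treatment phase (SP III), for example because another preventive agent is needed (Protocol 8.4.2 and 8.4.3), after which attack diary data are not collected (SAP 5.5.1). These rules apply to both arms and do not show that active patients would do worse. They are the reason the assumption needs testing.

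If every cell is significant, the reader learns that the result survives roughly equal imputed means, but not how much further it could go. A report could then call the result robust when a moderate, untested departure would overturn it.

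**Working it through.** **1. The SAP's own grid.** Upper Δ_P = 2 × |-3.6| = 7.2. The cap on Δ_A - Δ_P is |-1.5| = 1.5. Both match the SAP.

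**2. What the cap means.** Take missing patients as imputed near their arm means: placebo -3.6, active -3.6 - 1.5 = -5.1.

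- Δ_P = 0, Δ_A = 1.5: placebo -3.6, active -3.6.
- Δ_P = 7.2, Δ_A = 8.7: placebo +3.6, active +3.6.

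Return to baseline among missing active patients (Δ_A = 5.1) with placebo at MAR (Δ_P = 0) lies outside the grid. The grid is a diagonal band with area 7.2 × 1.5 = 10.8. The part of the rectangle (Δ_A 0 to 8.7, Δ_P 0 to 7.2) with Δ_A ≥ Δ_P has area 7.2 × 8.7 - 7.2²/2 = 36.72. The band covers 29% of it.

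**3. Inputs for an illustration.** From the SAP: the example values, 1:1 allocation and a one-sided 0.025 level (two-sided 0.05 below). The documents give no SD, final sample size or Week 1-3 missingness. Assumed: Weeks 2-3 missing in a share f of each arm; primary p under MAR of 0.02; 81, 60, 50 or 40 patients per arm. The first is the planned 162/2. Smaller values are shown because enrolment ended "prior to reaching the sample size target for the originally planned interim analysis" (SAP 3, Version 4).

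**4. Formulas**, with k = 2 missing weeks of 3:

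- Loss in the three-week difference = (k/3)(f_A Δ_A - f_P Δ_P)
- Variance per arm = SD² + f(1 - f)(kΔ/3)²
- t-test on 2n - 2 df, with SD set so that the unshifted p is 0.02 (SD 4.06, 3.48, 3.17, 2.82 for the four sample sizes)

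**5. Worked cells, n = 81 per arm, f = 10% in both arms.** Unshifted SE = 4.06 × √(2/81) = 0.638.

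- Corner (Δ_P 7.2, Δ_A 8.7): loss = (2/3)(0.87 - 0.72) = 0.10; difference 1.40, SE 0.686, t = 2.04, p = 0.043.
- Capped cell (Δ_P 0, Δ_A 1.5): loss = (2/3)(0.15) = 0.10; difference 1.40, SE 0.639, t = 2.19, p = 0.030.
- Untested cell (Δ_P 0, Δ_A 3.5): loss = (2/3)(0.35) = 0.233; difference 1.267, SE 0.643, t = 1.97, p = 0.051. Active imputed mean: -5.1 + 3.5 = -1.6, still better than baseline.

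With equal missingness, moving along the upper edge of the grid does not change the estimate. It only adds variance, which is why the corner is the worst cell.

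**6. Results at MAR p = 0.02** (values for n = 81/60/50/40 per arm):

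| Affected per arm | Largest p on the SAP grid | Δ_A that tips at Δ_P = 0 (cap 1.5) |
|---|---|---|
| 10% | 0.043 / 0.048 / 0.051 / 0.057 | 3.5 / 3.4 / 3.4 / 3.4 |
| 5% | 0.030 / 0.033 / 0.034 / 0.037 | 6.7 / 6.5 / 6.4 / 6.3 |
| 2% | 0.024 / 0.025 / 0.025 / 0.026 | 15.1 / 14.5 / 14.1 / 13.6 |

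**7. When the grid itself reacts.** It loses significance only if the primary p exceeds about 0.025/0.022/0.019/0.015 (10% affected) or 0.037/0.034/0.033/0.031 (5% affected). Below those values every cell stays significant and the distance to tipping is not shown.

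**8. Check by simulation.** Within-arm multiple imputation (30 imputations, Rubin's rules, assumed within-patient correlation 0.7, Weeks 2-3 missing, complete-data p = 0.02, median of 150 replicates) agrees. With 10% affected and n = 80/60/50/40, the corner gives p = 0.046/0.050/0.053/0.062. At Δ_P = 0, Δ_A = 1.5 gives 0.031 to 0.034 and Δ_A = 3.5 gives 0.053 to 0.056.

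**9. Cruder cross-check.** Hold the SE fixed and take 9.9% of active patients as missing all three weeks. The tipping value at Δ_P = 0 is (1.5 - 1.96 × 1.5/z)/0.099: 1.66, 3.28, 5.27 and 6.68 for z = 2.2, 2.5, 3.0 and 3.5, all above the cap. At z = 2.2 with 15% or 20% missing it falls to 1.09 or 0.82, inside the cap.

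**The case against.** The SAP does set a limit in advance, and it is interpretable: missing active patients may lose the whole observed benefit. Nothing in the documents promises a tipping-point analysis, so where to stop could be called a matter of preference.

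The grid also has force. Active penalties reach 8.7 in the example, and borderline results fail on it. With 10% affected on active and 5% on placebo, a primary p of 0.003 moves to 0.035/0.041/0.045/0.051 at the four sample sizes. A patient who leaves after a bad observed week is already imputed below the arm average, so a penalty can take that patient below placebo.

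The illustration may overstate missingness. The only attrition figure, (162 - 146)/162 = 9.9%, is planned non-completion over the whole study including 16 weeks of follow-up, whereas the primary window ends at Day 21. At 2% affected, tipping needs active patients at +8.5 to +10.0 attacks a week against baseline while missing placebo patients keep a 3.6 improvement, which few would find plausible. A smaller effect also lies nearer the threshold, so the narrower band is partly offset.

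All of this stands as a limit on importance, and the imputation point makes equality of imputed means approximate. It does not supply the missing information. A plan that stops at the observed effect cannot distinguish a result that tips at 3.5 from one that tips at 15 when both pass every cell.

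**Conclusion.** The concern holds, as an improvement to consider rather than a defect in the primary analysis. The cap, the untested region and the absence of a rule to reach a tipping point are all plain in the readable text of SAP 5.5.11, and no other readable analysis varies the MAR assumption.

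The practical size cannot be fixed from the documents. It is material when the primary result is moderate and around 5% to 10% of patients lack Weeks 2-3. At p = 0.02 with 10% affected, the full grid passes at 81 per arm (largest p 0.043; simulation at 80 per arm 0.046) and is close to the limit at 60 (0.048; simulation 0.050), yet Δ_A of about 3.5 at Δ_P = 0 overturns the result. It is small when few values are missing or the result is strong. At p = 0.003 with 10% affected in each arm, the largest grid p is 0.013 to 0.024 and tipping needs Δ_A of 6.6 to 7.1. The figures rest on the SAP's example values, equal missingness except where stated, and the assumed p-values and sample sizes.

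**What to change.** Keep Δ_P from 0 to twice the absolute placebo mean change, and keep Δ_A ≥ Δ_P. At each Δ_P, including 0, continue increasing Δ_A beyond the present cap until the primary comparison is no longer significant or a limit prespecified as implausible is reached. State the step size and that limit before unblinding. Report the tipping contour next to the number of patients and weeks imputed in each arm, so the reader can judge whether the tipping values are credible.

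The cost is more Δ_A values in the same multiple-imputation program and some extreme cells to interpret. The primary test, its type I error and the existing grid cells do not change. SAP 5.5.1 allows changes that are not principal features of the protocol to be described in the SAP or the study report without a protocol amendment.
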